### **6.4. Study Intervention Compliance**

When participants are dosed at the site, they will receive study intervention directly from the investigator or designee, under medical supervision. The date and time of each dose administered in the clinic will be recorded in the source documents and recorded in the DCT. Study site personnel will examine each participant's mouth to ensure that the study intervention was ingested.

### **6.5. Dose Modification**

Dose modification is not allowed in this study.

### **6.6. Continued Access to Study Intervention After the End of the Study**

No intervention will be provided to study participants at the end of their study participation.

### **6.7. Treatment of Overdose**

For this study, any dose of abrocitinib greater than 800 mg within a 24-hour time period ( $\pm 12$  hours) will be considered an overdose.

The sponsor does not recommend specific treatment for an overdose for abrocitinib. Observation and if required, supportive care would be expected.

In the event of an overdose, the investigator should:

1. Contact the medical monitor within 24 hours.
2. Closely monitor the participant for any AEs/SAEs and laboratory abnormalities for at least 5 half-lives or 28 calendar days after the overdose of abrocitinib (whichever is longer).
3. Document the quantity of the excess dose as well as the duration of the overdose in the DCT.
4. Overdose is reportable to Pfizer Safety **only when associated with an SAE**.
5. Obtain a blood sample for PK analysis within 3 days from the date of the last dose of study intervention if requested by the medical monitor (determined on a case-by-case basis).

Decisions regarding dose interruptions or modifications will be made by the investigator in consultation with the medical monitor based on the clinical evaluation of the participant.

## **6.8. Concomitant Therapy**

Use of prescription or nonprescription drugs and dietary and herbal supplements are prohibited within 7 days or 5 half-lives (whichever is longer) prior to the first dose of study intervention.

Vaccines with live components (or live attenuated vaccines) are prohibited within the 6 weeks prior to the first dose of abrocitinib, during the study treatment and during the 6 weeks following the discontinuation of abrocitinib.

Limited use of nonprescription medications that are not believed to affect participant safety or the overall results of the study may be permitted on a case-by-case basis following approval by the sponsor. Acetaminophen/paracetamol may be used at doses of  $\leq 1$  g/day.

Hormonal contraceptives that meet the requirements of this study are allowed to be used in participants who are WOCBP (see [Appendix 4](#)).

All concomitant treatments taken during the study must be recorded with indication, daily dose, and start and stop dates of administration. All participants will be questioned about concomitant treatment at each clinic visit.

Treatments taken within 28 days before the first dose of study intervention will be documented as a prior treatment. Treatments taken after the first dose of study intervention will be documented as concomitant treatments.

### **6.8.1. Rescue Medicine**

There is no rescue therapy to reverse the AEs observed with abrocitinib; standard medical supportive care must be provided to manage the AEs.

## **7. DISCONTINUATION OF STUDY INTERVENTION AND PARTICIPANT DISCONTINUATION/WITHDRAWAL**

### **7.1. Discontinuation of Study Intervention**

It may be necessary for a participant to permanently discontinue study intervention. Reasons for permanent discontinuation of study intervention include the following:

- AE requiring discontinuation in investigator's view;
- Pregnancy;
- Positive COVID-19 test.

If study intervention is permanently discontinued, the participant will not remain in the study for further evaluation. See the [SoA](#) for data to be collected at the time of discontinuation of study intervention.

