For a participant who completes both Parts A and B of the study, the expected duration of participation from screening in Part A to the follow-up telephone contact in Part B of the study is approximately 11 weeks. While for a participant who completes only Part A or Part B of the study, the expected duration of participation from screening to the follow-up telephone contact is approximately 10 weeks. Participants who discontinue the study may be replaced at the sponsor's discretion. The replacement participant will receive the same treatment sequences as the participant who discontinued.

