**Table 2. Schedule of Activities (Part B)**

Visit Identifier a Abbreviations used in this table may be found in Appendix 9: Abbreviations	Period 4		Period 5	Period 6	Period 7	Period 8	Period 9		Early Termination/ DC	Follow-up b
Days Relative to Day 1	Day -1 c	Day 1	Day 1	Day 1	Day 1	Day 1	Day 1	Day 2		28-35 Days
Informed consent d										
CRU confinement	→	→	→	→	→	→	→	X	X	
Inclusion/exclusion criteria d										
Physical examination e								X	X	
Safety laboratory f	X							X	X	
Pregnancy test for WOCBP only								X	X	
Contraception check for WOCBP only	X							X	X	X
Single 12-Lead ECG		X g						X	X	
Supine BP, pulse rate, and oral temperature	X	X h						X	X	
COVID-19 testing					X i					
COVID-19 check temperature j	X	X	X	X	X	X	X			
Study treatment administration		X	X	X	X	X	X			
Taste Assessment Questionnaire k	X	X	X	X	X	X				
CCI										
CRU discharge								X	X	
Serious and nonserious AE monitoring		→	→	→	→	→	→	→	→	X
Prior/concomitant treatments		→	→	→	→	→	→	→	→	X

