**Table 2. Schedule of Activities (Part B)**

Visit Identifier a Abbreviations used in this table may be found in Appendix 9: Abbreviations	Period 4		Period 5	Period 6	Period 7	Period 8	Period 9		Early Termination/ DC	Follow-up b
Days Relative to Day 1	Day -1 c	Day 1	Day 1	Day 1	Day 1	Day 1	Day 1	Day 2		28-35 Days

- a. Day relative to the first day of study intervention dosing in all periods.
- b. Contact may occur via telephone contact and must occur 28 to 35 days from administration of the final dose of study intervention, either in Parts A (in case of early termination/DC) or in Part B of the study.
- c. Day -1 of Period 4 in Part B of the study overlaps with Day 3 of Period 3 in Part A of the study.
- d. For new participants enrolled in Part B only, all Screening and Day -1 visit procedures will be performed as listed in [Table 1](#) SoA (Part A).
- e. A complete physical examination will be done at screening or may be deferred to Day -1 of Period 4 at the discretion of the investigator for new participants admitting for Part B only of the study. A complete physical examination should be performed on Day 2 of Period 9 or at the Early Termination/DC visit (if this occurs). A brief physical examination can be performed at other times if findings during the previous examination or new/open AE, at the discretion of the investigator.
- f. Section 8.2.4 Safety laboratory test assessments consist of hematology, urinalysis, and clinical chemistry. For details on the tests to be performed, please refer to protocol [Appendix 2](#). The safety tests will be performed at screening, Day-1 of Period 4, each admission to CRU, at study discharge, and early withdrawal. All assessments must be collected following at least a 4-hour fasting period. Samples will be collected if the reason for DC is related to an AE. Additional assessments may be performed at the discretion of the investigator.
- g. To be collected at predose of abrocitinib for new participants enrolled in Part B only.
- h. To be collected at predose and 1-hour postdose (around  $T_{max}$ ) of abrocitinib.
- i. For new participants joining this part of the study, and admitted for residence, a subsequent COVID-19 test will be performed after 4 days (ie, upon completion of  $4 \times 24$  hours in-house), or if they develop COVID-19 like symptom(s).
- j. To be done at least daily during residence.

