### **7.2. Participant Discontinuation/Withdrawal From the Study**

A participant may withdraw from the study at any time at his/her own request. Reasons for discontinuation from the study include the following:

- Refused further study procedures;
- Lost to follow-up;
- Death;
- Study terminated by sponsor;
- Behavioral, compliance or administrative reasons.

At the time of discontinuing from the study, if possible, an early discontinuation visit should be conducted. See the [SoA](#) for assessments to be collected at the time of study discontinuation and follow-up and for any further evaluations that need to be completed.

If a participant withdraws from the study, he/she may request destruction of any remaining samples taken and not tested, and the investigator must document any such requests in the site study records and notify the sponsor accordingly. If the participant withdraws from the study and also withdraws consent (see Section [7.2.1](#)) for disclosure of future information, no further evaluations should be performed and no additional data should be collected. The sponsor may retain and continue to use any data collected before such withdrawal of consent.

When a participant withdraws from the study because of an SAE, the SAE must be recorded on the DCT and reported on the CT SAE Report.

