### **7.2.1. Withdrawal of Consent**

Participants who request to discontinue receipt of study intervention will remain in the study and must continue to be followed for protocol-specified follow-up procedures. The only exception to this is when a participant specifically withdraws consent for any further contact with him or her or persons previously authorized by the participant to provide this information. Participants should notify the investigator in writing of the decision to withdraw consent from future follow-up, whenever possible. The withdrawal of consent should be explained in detail in the medical records by the investigator, as to whether the withdrawal is only from further receipt of study intervention or also from study procedures and/or posttreatment study follow-up, and entered on the appropriate DCT page. In the event that vital status (whether the participant is alive or dead) is being measured, publicly available information should be used to determine vital status only as appropriately directed in accordance with local law.

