#### **8.3.1. Time Period and Frequency for Collecting AE and SAE Information**

The time period for actively eliciting and collecting AEs and SAEs (“active collection period”) for each participant begins from the time the participant provides informed consent, which is obtained before the participant’s participation in the study (ie, before undergoing any study-related procedure and/or receiving study intervention), through and including a minimum of 28 calendar days after the last administration of the study intervention.

Follow-up by the investigator continues throughout and after the active collection period and until the AE or SAE or its sequelae resolve or stabilize at a level acceptable to the investigator.

For participants who are screen failures, the active collection period ends when screen failure status is determined.

If the participant withdraws from the study and also withdraws consent for the collection of future information, the active collection period ends when consent is withdrawn.

If a participant permanently discontinues or temporarily discontinues study intervention because of an AE or SAE, the AE or SAE must be recorded on the DCT and the SAE reported using the CT SAE Report Form.

Investigators are not obligated to actively seek information on AEs or SAEs after the participant has concluded study participation. However, if the investigator learns of any SAE, including a death, at any time after a participant has completed the study, and he/she

considers the event to be reasonably related to the study intervention, the investigator must promptly report the SAE to Pfizer using the CT SAE Report Form.

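### Section 7.1 takes permanently discontinued participants out of the study, against the 28-day AE collection and 28 to 35 day contact required elsewhere

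*Protocol*

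**What the plan says.** Section 7.1 introduces three reasons for permanently stopping study intervention (an AE that in the investigator's view requires it, pregnancy, a positive COVID-19 test) and then states: "If study intervention is permanently discontinued, the participant will not remain in the study for further evaluation". Its next sentence refers to the Schedule of Activities, but only for data due when dosing is discontinued.

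Other parts of the protocol set a later end point:

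- Section 8.3.1 runs active AE and SAE collection in each participant from consent "through and including a minimum of 28 calendar days after the last administration of the study intervention". It names two early endings. One is screen failure. The other is withdrawal from the study together with withdrawal of consent to future data collection, in which case "the active collection period ends when consent is withdrawn".
- Table 2 footnote b applies to both parts of the study. It says the follow-up contact, which may be by telephone, "must occur 28 to 35 days from administration of the final dose of study intervention, either in Parts A (in case of early termination/DC".
- Section 7.2, on leaving the study, refers to the Schedule of Activities "for assessments to be collected at the time of study discontinuation and follow-up and for any further evaluations that need to be completed".
- Section 7.2.1 says that participants who ask to stop study intervention "will remain in the study and must continue to be followed for protocol-specified follow-up procedures", unless they withdraw consent for any further contact.

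SAP Section 6.2 counts an event as treatment-emergent if it starts before the last dose plus 28 days.

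**The concern.** Section 7.1 is where a site looks when it stops someone's dosing, and it says that the person leaves the study. Two other features make a literal reading plausible. Section 8.3.1 also relieves investigators of the duty to seek AEs actively once a participant has concluded participation, and a site could take 7.1 as the point at which that happens. And Table 1, the Part A schedule, has no follow-up column; the instruction covering Part A discontinuers appears only in a footnote to the Part B schedule.

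At stake is the detection of new events in people whose dosing was stopped, in some cases because of an AE. Safety and tolerability is a secondary objective in both parts. If the contact is skipped, the SAP's 28-day window still exists on paper, but for that participant no scheduled check covers the time after the early termination visit.

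**Working it through.** The plan states no figure to reproduce. The check is a comparison of the provisions, followed by a bound on what could be lost.

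**Step 1. Does each provision conflict with 7.1?**

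| Provision | Who it covers | What it requires | Conflict with 7.1 |
|---|---|---|---|
| 8.3.1 | Each participant | AE/SAE collection to at least 28 days after last dose; investigator-led discontinuation is not listed as an early ending | Direct |
| Table 2, footnote b | Includes early termination in Part A | Mandatory contact at 28 to 35 days | Direct |
| 7.2.1 | Participants who ask to stop dosing | Stay in the study and be followed | Indirect: a different route to stopping, although the 7.1 sentence applies to any permanent discontinuation and its list of reasons is not closed |

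**Step 2. Which side reflects the intention?** Section 7.2 expects follow-up after someone leaves the study. In both schedules the row "Serious and nonserious AE monitoring" carries an arrow in the early termination column, and Appendix 9 defines the arrow as an ongoing event. In Table 2 the same row has an X at follow-up. The SAP window also ends at last dose plus 28 days. All of this points to follow-up being planned, with 7.1 as the outlier.

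**Step 3. What does the contact carry?** The rows of Table 2 marked in the follow-up column are AE monitoring, prior/concomitant treatments, and the contraception check. The last applies to women of childbearing potential (WOCBP) only. So:

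- man, or woman not of childbearing potential: 2 checks;
- WOCBP: 3 checks.

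Let d be the number permanently discontinued whose contact is omitted, and w the number of those who are WOCBP. Then checks lost = 2d + w, which lies between 2d and 3d. With d = 0 nothing is lost; with d = 1 the loss is one contact and 2 or 3 checks. The documents give no discontinuation rate, so d is unknown.

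**Step 4. What is protected regardless?**

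- AEs already reported are followed to resolution or stabilisation (8.3.3).
- Known pregnancies are followed to outcome (8.3.5.1).
- Clinically significant laboratory abnormalities found during participation or within 28 days after the last dose are repeated until resolved (8.2.4).
- A contraception check and pregnancy test are also scheduled at the early termination visit.

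What remains exposed is a new AE not yet reported, late concomitant treatments, and the contraception check at the end of the 28-day period required by Section 5.1.

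**Step 5. Are other analyses affected?** No. The contact collects neither pharmacokinetic samples nor taste questionnaires.

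**The case against.** The strongest reply is that the sections can be read in sequence. A participant stopped under 7.1 passes to 7.2, which asks for an early discontinuation visit if possible and refers to the schedule for follow-up; the schedule then makes the contact mandatory. On this reading the evaluation that ends under 7.1 is only the remaining treatment-period assessments. That is probably what was meant, but 7.1 does not say so: it removes the participant from the study, not merely from later periods, and its own reference to the schedule stops at the time of discontinuation.

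Three parts of the reply stand. Section 7.2.1 concerns people who ask to stop, so it does not carry the same weight as 8.3.1 and footnote b. The contraception check should not be counted for everyone. And the duration text, under which "the expected duration of participation from screening to the follow-up telephone contact is approximately 10 weeks", describes participants who complete Part A or Part B; it says nothing about those stopped early and is not relied on here.

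A reader might go further and infer that the trial has no safety follow-up for discontinued participants, or that those stopped for an AE are dropped by design while those who stop by choice are kept. The documents do not support either. Both inferences require 7.1 to override 7.2, 8.3.1 and footnote b, and those provisions show that the contact is planned.

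**Conclusion.** The inconsistency is real and is a drafting error in 7.1; the follow-up design itself is sound. It conflicts directly with 8.3.1 and Table 2 footnote b, and less directly with 7.2.1.

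The consequence is small and conditional: at most one omitted contact, with 2 or 3 checks, for each permanently discontinued participant, and only where a site lets 7.1 prevail over the mandatory wording elsewhere. Participants who complete Part B are discharged on Day 2 of Period 9, one day after their last dose, and depend on the same single contact, so the only difference for discontinuers is the risk that it is not made. Only the descriptive safety data could be affected. The conclusion assumes nothing about how many will discontinue, and the number affected may be zero. This is a low-priority correction, worth making because it costs little and concerns people who may have been stopped for a safety reason.

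**What to change.** Replace the 7.1 sentence with:

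> *If study intervention is permanently discontinued, the participant will receive no further doses or treatment periods. Unless consent for further contact is withdrawn, an Early Termination/DC visit should be conducted if possible, and the follow-up contact 28 to 35 days after the last dose and AE/SAE collection to at least 28 days after the last dose will be completed.*

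This keeps the conditional visit wording of 7.2 and applies the consent exception to the visit, the contact and the AE collection alike.

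Optionally, add a cross-reference under Table 1 to Table 2 footnote b, so that a reader of the Part A schedule finds the contact.

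The cost is a wording change, made in a protocol amendment (with whatever ethics review Section 10.1.1 then requires) or a clarification to the site. There is no added visit or contact, and SAP Section 6.2 needs no change because it already uses last dose plus 28 days.

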### **7.2. Participant Discontinuation/Withdrawal From the Study**

A participant may withdraw from the study at any time at his/her own request. Reasons for discontinuation from the study include the following:

- Refused further study procedures;
- Lost to follow-up;
- Death;
- Study terminated by sponsor;
- Behavioral, compliance or administrative reasons.

At the time of discontinuing from the study, if possible, an early discontinuation visit should be conducted. See the [SoA](#) for assessments to be collected at the time of study discontinuation and follow-up and for any further evaluations that need to be completed.

If a participant withdraws from the study, he/she may request destruction of any remaining samples taken and not tested, and the investigator must document any such requests in the site study records and notify the sponsor accordingly. If the participant withdraws from the study and also withdraws consent (see Section [7.2.1](#)) for disclosure of future information, no further evaluations should be performed and no additional data should be collected. The sponsor may retain and continue to use any data collected before such withdrawal of consent.

When a participant withdraws from the study because of an SAE, the SAE must be recorded on the DCT and reported on the CT SAE Report.

### **7.2.1. Withdrawal of Consent**

Participants who request to discontinue receipt of study intervention will remain in the study and must continue to be followed for protocol-specified follow-up procedures. The only exception to this is when a participant specifically withdraws consent for any further contact with him or her or persons previously authorized by the participant to provide this information. Participants should notify the investigator in writing of the decision to withdraw consent from future follow-up, whenever possible. The withdrawal of consent should be explained in detail in the medical records by the investigator, as to whether the withdrawal is only from further receipt of study intervention or also from study procedures and/or posttreatment study follow-up, and entered on the appropriate DCT page. In the event that vital status (whether the participant is alive or dead) is being measured, publicly available information should be used to determine vital status only as appropriately directed in accordance with local law.

### **7.3. Lost to Follow-up**

A participant will be considered lost to follow-up if he or she repeatedly fails to return for scheduled visits and is unable to be contacted by the study site.

The following actions must be taken if a participant fails to return to the clinic for a required study visit:

- The site must attempt to contact the participant and reschedule the missed visit as soon as possible. Counsel the participant on the importance of maintaining the assigned visit schedule, and ascertain whether the participant wishes to and/or should continue in the study;
- Before a participant is deemed lost to follow-up, the investigator or designee must make every effort to regain contact with the participant (where possible, 3 telephone calls and, if necessary, a certified letter to the participant's last known mailing address or local equivalent methods). These contact attempts should be documented in the participant's medical record;
- Should the participant continue to be unreachable, he/she will be considered to have withdrawn from the study.

